4.4.1.3 SAEs

4.4.1.3.1 Last Vaccination

Last vaccination before an SAE is derived from the last visit numbers provided in the clinical database and is calculated as follows:

- If an SAE has a non-missing visit number, the visit number should be used to determine the last vaccination before the SAE
- If the visit number is missing, then the start date should be used to determine the last vaccination before the SAE

4.4.1.3.2 Time of Onset

Time of onset will be computed using the same methodology as for unsolicited non-serious AEs described in [Section 4.4.1.2.4](#).

SAEs will be analyzed throughout the study using the following periods:

- Within 30 days
- During the study (i.e., all SAEs occurred during the study)

An SAE with missing time of onset will be considered to have occurred just after the vaccination indicated by the visit number, so will be included in these tables.

Note: SAEs that occurred before vaccination (negative time of onset) will not be included in analysis, but will be listed separately.

4.4.1.3.3 Duration

Duration will be computed using the same methodology as for unsolicited non-serious AEs described in [Section 4.4.1.2.5](#).

4.4.1.4 Other Safety Endpoints

4.4.1.4.1 Pregnancy

Not applicable for this study.

4.4.1.4.2 Action Taken

This information will be summarized as collected, including missing observations. No derivation or imputation will be done.

4.4.1.4.3 Seriousness

This information will be summarized as collected. No derivation or imputation will be done.

4.4.1.4.4 Outcome

This information will be summarized as collected. No derivation or imputation will be done.

4.4.1.4.5 Causality

This information will be summarized as collected. Missing causality (relationship) will be handled as described in [Section 5.3.1.2](#).

4.4.1.4.6 AEs Leading to Study Discontinuation

A flag is available in the clinical database for all AEs in order to identify AEs leading to discontinuation.

In general, the items that are counted are:

- Disposition table: A subject who has, on the termination form, the reason for early termination “Serious Adverse Event” or “Other adverse event” checked
- Safety overview table: A subject who has either on the termination form, the reason for early termination “Serious Adverse Event” or “Other adverse event” checked or lists an AE on an AE page (solicited, unsolicited, or SAE) that has “Reaction Leading to Termination” or “Event Leading to Termination” or “Serious Adverse Event Leading to Termination” checked that is at least Grade 1 and is within the time period indicated
- System Organ Class/Preferred Term (SOC/PT) table: An event (solicited, unsolicited, or SAE) that has “Reaction Leading to Termination” or “Event Leading to Termination” or “Serious Adverse Event Leading to Termination” checked that is at least Grade 1 and is within the time period indicated

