### 9.3.2.2 Safety Endpoints

The observational endpoints for the evaluation of safety are:

- Occurrence, nature (Medical Dictionary for Regulatory Activities [MedDRA] preferred term), duration, intensity, and relationship to vaccination of any unsolicited systemic AEs reported in the 30 minutes after vaccination.
- Occurrence, time of onset, number of days of occurrence, intensity, action taken, and whether the reaction led to early termination from the study, of solicited (prelisted in the subject's diary card and electronic CRF) injection site reactions occurring up to 7 days after vaccination
- Occurrence, time of onset, number of days of occurrence, intensity, action taken, and whether the reaction led to early termination from the study, of solicited (prelisted in the subject's diary card and CRF) systemic reactions occurring up to 7 days after vaccination.
- Occurrence, nature (MedDRA preferred term), time of onset, duration, intensity, action taken, relationship to vaccination (for systemic AEs only), and whether the event led to early termination from the study, of unsolicited AEs up to Visit 2 after vaccination.
- Occurrence, nature (MedDRA preferred term), time of onset, duration, seriousness criteria, relationship to vaccination, outcome, and whether the SAE led to early termination from the study of SAEs, [REDACTED], throughout the trial.

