4.4.1.2.2 Intensity

Intensity for unsolicited non-serious adverse event (AE) will be derived according to the following classification: None, Grade 1, Grade 2, Grade 3, or Missing.

If the unsolicited non-serious AE is measurable and its preferred term is part of the list of solicited reactions, then the measurement is derived based upon and following the same rule than the intensity scales defined in the protocol for that measurable injection site or systemic reaction.

Intensity for the other unsolicited non-serious AEs will correspond to the value reported in the CRF.

The maximum intensity corresponds to the highest intensity for a unique term.

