5.3.1.4 Intensity

For solicited reactions, missing intensities will be handled as described in [Section 4.4.1.1.1](#). For unsolicited non-serious AEs, missing intensities will remain missing and will not be imputed.

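### The Grade 1 threshold for events leading to discontinuation cannot be met by SAEs, for which the documents provide no intensity grade, so flagged SAEs can be missing from the SOC/PT table

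*SAP*

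**What the plan says.** SAP 4.4.1.4.6 gives counting rules for three tables.

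- **Disposition table.** A subject counts if the termination form gives an SAE or another AE as the reason. No grade is required.
- **Safety overview table.** There are two routes. The first is the form: "A subject who has either on the termination form, the reason for early termination" is an SAE or another AE. The second is an event page (solicited, unsolicited or SAE) with its leading-to-termination box ticked, and here the event must also be at least Grade 1 and inside the period.
- **SOC/PT table.** There is only the event-page route: "System Organ Class/Preferred Term (SOC/PT) table: An event (solicited, unsolicited, or SAE) that has" its termination box ticked and "that is at least Grade 1 and is within the time period indicated".

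The SAE endpoint in Protocol 9.3.2.2 reads "Occurrence, nature (MedDRA preferred term), time of onset, duration, seriousness criteria, relationship to vaccination, outcome, and whether the SAE led to early termination". Intensity is not in that list, although the solicited and unsolicited endpoints beside it do include it.

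On grading, SAP 4.4.1.2.2 states: "Intensity for unsolicited non-serious adverse event (AE) will be derived according to the following classification", with Missing as one of the classes. SAP 5.3.1.4 adds: "For unsolicited non-serious AEs, missing intensities will remain missing and will not be imputed".

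**The concern.** The SOC/PT bullet brings SAEs into scope and then sets a condition for which they have no data. A programmer who applies it literally would drop any flagged SAE that has no grade. The same happens to a flagged unsolicited non-serious AE with missing intensity, because that value stays missing by rule.

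Whether an SAE led to early termination is part of a protocol endpoint. Protocol 12.1.3 and SAP 5.1.3.2 also promise a separate tabulation of events leading to withdrawal. The SOC/PT table is the one that names those events by MedDRA term. A child who stopped because of an SAE could be counted as such in the disposition and overview tables and have no matching SOC/PT row. Single events carry weight in a table like this, so even one missing row would raise a query.

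**Working it through.** No arithmetic applies. The check traces where each type of record could get a grade and then applies the SOC/PT rule to it.

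| Flagged record | Source of a grade | If the grade is absent | Result under the SOC/PT rule |
|---|---|---|---|
| Solicited reaction | Protocol Tables 9.1 and 9.2; SAP 4.4.1.1.1 | SAP 4.4.1.1.3: presence is missing | Counted if Grade 1 to 3 |
| Unsolicited non-serious AE, graded | Protocol 9.3.2.3.3; SAP 4.4.1.2.2 | Not applicable | Counted if Grade 1 to 3 |
| Unsolicited non-serious AE, grade missing | As above | SAP 5.3.1.4: stays missing | Not counted |
| SAE | None found | No rule | Not counted |

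**SAEs.** Five places could have supplied a grade, and none does:

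1. Protocol 9.3.2.2 lists seriousness criteria, relationship and outcome for SAEs, but not intensity.
2. Protocol 9.3.2.3.4, on SAE collection, does not mention intensity.
3. SAP 4.4.1.3 derives only last vaccination, time of onset and duration.
4. SAP 4.4.1.2.2 limits its derivation to non-serious events.
5. SAP 5.3.1.4 covers missing intensity only for solicited reactions and unsolicited non-serious AEs.

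A grade cannot be inferred from seriousness either, because Protocol 9.3.2.1 says that serious and severe mean different things.

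**Unsolicited non-serious AEs with no grade.** SAP 4.4.1.2.1 counts a record as an event if it has a verbatim term and is not Grade 0, so a missing grade does not disqualify it. The discontinuation rule is stricter and would remove the same record.

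**Other missing values.** The SAP generally keeps an event when a value is absent. Missing causality counts as related (5.3.1.2), and AEs or SAEs with missing onset stay in the tables (4.4.1.2.4, 4.4.1.3.2, 5.3.1.5). The discontinuation rule goes against that convention.

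**Across the three tables.** Take a subject with a flagged, ungraded SAE and SAE given as the reason on the termination form. The disposition table counts the subject, the overview counts the subject through the form, and the SOC/PT table has no row. If the form gave some other reason, the overview would miss the subject too, because its event-page route carries the same threshold.

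**The case against.** **The absence of an SAE grade is inferred.** No sentence says that SAEs are ungraded, and the CRF and SAE form are not among the documents. By the definitions in Protocol 9.3.2.1, unsolicited AEs include SAEs. The unsolicited endpoint lists intensity without restriction to non-serious events, and SAP 5.1.3.2 tabulates unsolicited AEs by intensity. This stands as a caution. It does not remove the problem, because none of these places says how an SAE would be graded.

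**The intent is plain.** The bullet names SAEs and their termination flag, which would be pointless if no SAE could qualify, and the list is introduced as a general guide. The threshold was probably meant to drop Grade 0 records. That is likely right, and it makes this a wording error rather than a decision to exclude SAEs. The text still has to be programmed.

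**A reader might infer that every SAE discontinuation disappears.** The documents do not support that. A serious event that is also a solicited reaction could enter through its graded solicited record; the solicited action scale in Protocol 9.3.2.3.2 includes inpatient hospitalization. SAEs are tabulated separately with preferred term and outcome, and the disposition table and termination-form route need no grade. SAE is also the top-ranked termination reason in Protocol 5.2.11, so the form should usually capture it.

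**The overview and SOC/PT tables differ by design.** One counts subjects, partly from the form, and the other counts flagged events. This is true, but it does not explain why a named class of event should have no rows.

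**Conclusion.** The point holds as a specification error in SAP 4.4.1.4.6. As written, two kinds of flagged record cannot enter the SOC/PT table or use the event-page route of the overview: an SAE without a graded solicited record, and an unsolicited non-serious AE with missing intensity. The conclusion on SAEs assumes that no grade is collected on forms outside these documents. If one is, the defect for SAEs reduces to an unstated source.

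The effect is confined to descriptive safety tables. It touches no hypothesis, primary endpoint or collection of safety data. The number of records should be very small and may be zero: Protocol 1.2.2.2 reports no discontinuations due to an SAE or other AE after MenACYW in MET54. A reader might want to turn that zero into an upper bound on the records lost here. It would not be one. It would bound all AE discontinuations, most of which could be graded and unaffected, and the safety summary gives no denominator. No numerical range is therefore offered.

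**What to change.** In the safety overview and SOC/PT bullets of SAP 4.4.1.4.6, keep the time-period condition for every record and replace the single grade threshold with one rule per record type:

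- **Solicited reactions:** Grade 1 or higher, as now. This agrees with SAP 4.4.1.1.3, where missing intensity means missing presence, so ungraded solicited records should not be admitted.
- **Unsolicited non-serious AEs:** any grade other than Grade 0, with missing intensity counted. This agrees with SAP 4.4.1.2.1.
- **SAEs flagged as leading to termination:** counted regardless of intensity.

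If the SAE form does collect a grade, the SAP should also name that source.

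The cost is about one sentence in each bullet and a small change to the selection code. No record that now qualifies would be removed, and no collected data change.

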4.4.2 Immunogenicity

4.4.2.1 Computed Values for Analysis

In order to appropriately manage extreme values ($<$ the lower limit of quantitation [LLOQ] and \geq the upper limit of quantitation [ULOQ]) for analysis purposes, the following computational rule is applied to the values provided in the clinical database for each BL drawn:

- If a value is $<$ LLOQ, then use the computed value $LLOQ/2$
- If a value is between \geq LLOQ and $<$ ULOQ, then use the value
- If a value is \geq ULOQ, then use the computed value ULOQ

4.4.2.2 Fold-rise

The derived endpoint fold-rise is driven by both baseline and post-baseline computed values and is computed as follows:

- Calculate the fold-rise of values as the ratio of post-baseline computed value divided by baseline computed value

Note: If baseline or post-baseline is missing, then fold-rise is missing.

4.4.2.3 hSBA Vaccine Seroreponse

The derived seroreponse indicator for hSBA will be “Yes” if

- hSBA titer is $<$ 1:8 at baseline with a post-baseline hSBA titer \geq 1:16
- or hSBA titer is \geq 1:8 at baseline with a \geq 4-fold increase at post-baseline

4.4.2.4 rSBA Vaccine Seroreponse

The derived seroreponse indicator for rSBA will be “Yes” if

- rSBA titer is $<$ 1:8 at baseline with a post-baseline rSBA titer \geq 1:32
- or rSBA titer is \geq 1:8 at baseline with a \geq 4-fold increase at post-baseline

4.4.2.5 Efficacy

Not applicable

4.4.3 Derived Other Variables

4.4.3.1 Age for Demographics

The age of a subject in the study was the calendar age in months at the time of inclusion.

4.4.3.2 Duration of a Subject in the Trial

The duration of a subject in the study is computed as follows:

Maximum (date of last visit, date of termination) – (date of Visit 1 of that subject) + 1.

4.4.3.3 Duration of the Study

The duration of the study is computed as follows:

Maximum of all subjects (date of last visit, date of termination) – Minimum of all subjects (date of Visit 1) + 1.

5 Statistical Methods and Determination of Sample Size

The statistical analyses will be performed under the responsibility of the Sponsor's Biostatistics platform using SAS[®] Version 9.4 software or later.

The results of the statistical analysis will be available in the final clinical study report. For descriptive purposes, the following statistics will be presented:

Table 5.1: Descriptive statistics produced

Baseline characteristics and follow-up description	Categorical data	Number of subjects. Percentage of subjects.
	Continuous data	Mean, standard deviation, quartiles, minimum, and maximum.
Clinical safety results	Categorical data	Solicited: Number and percentage (95% CIs) of subjects. Unsolicited: Number and percentage (95% CIs) of subjects, and number of events.
Immunogenicity results	Categorical data (seroresponse, ≥ 4 fold rise, cutoff)	Number and percentage (95% CIs) of subjects.
	Continuous data (titer / concentration)	Log ₁₀ : Mean and standard deviation. Anti-Log ₁₀ (work on Log ₁₀ distribution, and anti-Log ₁₀ applied): Geometric mean (GM), 95% CI of the GM. Graphical representation by Reverse Cumulative Distribution Curve (RCDC).

The confidence interval (CI) for the single proportion will be calculated using the exact binomial method (Clopper-Pearson method, quoted by Newcombe (1)). For immunogenicity results, assuming that Log₁₀ transformation of the titers follows a normal distribution, at first, the mean and the 95% CI will be calculated on Log₁₀ (titers) using the usual calculation for normal distribution (using Student's t distribution with n-1 degree of freedom), then antilog transformations will be applied to the results of calculations, in order to provide GMs and their 95% CI.

5.1 Statistical Methods

5.1.1 Hypotheses and Statistical Methods for Primary Objectives

Two co-primary objectives will be evaluated.

5.1.1.1 Hypotheses

5.1.1.1.1 Hypothesis for Co-primary Objective 1

Co-primary hypothesis 1: Non-inferiority testing after 1 dose of MenACYW conjugate vaccine or Nimenrix® in toddlers who either are meningococcal vaccine naïve or have received monovalent MenC vaccination during infancy

The percentages of subjects who achieve an hSBA titer $\geq 1:8$ for meningococcal serogroups A, C, Y, and W in toddlers who received MenACYW conjugate vaccine (Group 1 and Group 3) are non-inferior to the corresponding percentages in toddlers who received Nimenrix® (Group 2 and Group 4) 30 days post administration.

Null hypothesis (H₀): $p_{(\text{Men})} - p_{(\text{Nim})} \leq -10\%$

Alternative hypothesis (H₁): $p_{(\text{Men})} - p_{(\text{Nim})} > -10\%$

where $p_{(\text{Men})}$ and $p_{(\text{Nim})}$ are the percentages of subjects who achieve an hSBA titer $\geq 1:8$ in the MenACYW vaccine group and the Nimenrix[®] group, respectively.

5.1.1.1.2 Hypothesis for Co-primary Objective 2

Co-primary hypothesis 2: Non-inferiority testing after 1 dose of MenACYW conjugate vaccine or Nimenrix[®] in meningococcal vaccine naïve toddlers

Thirty days after the administration of MenACYW conjugate vaccine or Nimenrix[®], the percentages of subjects who achieve an hSBA titer $\geq 1:8$ for meningococcal serogroups A, C, Y, and W in Group 1 are non-inferior to the corresponding percentages in Group 2.

Null hypothesis (H₀): $p_{(\text{G1})} - p_{(\text{G2})} \leq -10\%$

Alternative hypothesis (H₁): $p_{(\text{G1})} - p_{(\text{G2})} > -10\%$

where $p_{(\text{G1})}$ and $p_{(\text{G2})}$ are the percentages of subjects who achieve an hSBA titer $\geq 1:8$ in Group 1 and Group 2, respectively.

5.1.1.2 Statistical Methods

5.1.1.2.1 Statistical Method for Co-primary Objective 1

Each of the serogroups A, C, Y, and W will be tested separately. If the lower limit of the 2-sided 95% confidence interval (CI) of the difference between the 2 percentages is $> -10\%$, the inferiority assumption will be rejected.

For the 4 non-inferiority hypotheses using the response rates (percentages of subjects who achieve an hSBA titer $\geq 1:8$), the 95% CI will be stratified on the priming status (meningococcal vaccine naïve or primed monovalent MenC vaccination during infancy) and calculated using the Wald method (normal approximation). Weighted average of the difference over strata will be calculated using the Minimal Risk weights with the null variance method (2).

The 100(1- α)% two-sided CIs for the difference in proportions between two groups using the Minimum Risk Weights with the null variance are calculated as follows:

$$\hat{\delta}_w \pm Z_{\alpha/2} \sqrt{\left\{ \sum_{i=1}^s w_i^2 \hat{V}_0(\hat{\delta}_i) \right\}}$$

where $i=1,2, s=2, \hat{\delta}_w = \sum_{i=1}^s w_i \hat{\delta}_i = \sum_{i=1}^s w_i (\hat{P}_{iB} - \hat{P}_{iA}), \hat{P}_{iA}, \hat{P}_{iB}$ are the observed response rates for MenACYW vaccine group and the Nimenrix[®] group respectively at stratum $i, Z_{\alpha/2}$ is the 100(1-

$\alpha/2$)th percentile of the standard normal distribution, and w_i are the weight assigned at stratum i , and

$\hat{V}_0(\hat{\delta}_i) = \frac{\tilde{P}_{iA}(1-\tilde{P}_{iA})}{n_{iA}} + \frac{\tilde{P}_{iB}(1-\tilde{P}_{iB})}{n_{iB}}$ is the null variance, where $\tilde{P}_{iA}, \tilde{P}_{iB}$ are the constrained maximum likelihood estimates (MLEs) of response rates of MenACYW and Nimenrix at stratum i , and n_{iA}, n_{iB} are the sample sizes for MenACYW and Nimenrix at each stratum.

The Minimum Risk method computes the weights w_i as follows:

$$w_i = \frac{\beta_i}{\sum_{k=1}^s V_k^{-1}} - \left(\frac{\alpha_i V_i^{-1}}{\sum_{k=1}^s V_k^{-1} + \sum_{k=1}^s \alpha_k \delta_k V_k^{-1}} \right) \left(\frac{\sum_{k=1}^s \delta_k \beta_k}{\sum_{k=1}^s V_k^{-1}} \right)$$

where $\alpha_i = \delta_i \sum_{k=1}^s V_k^{-1} - \sum_{k=1}^s \delta_k V_k^{-1}$ and $\beta_i = V_i^{-1} \left(1 + \alpha_i \sum_{k=1}^s f_k \delta_k \right)$, $V_i = V(\hat{\delta}_i)$, and f_i is the fraction of subjects in the target population that belong in stratum i ($\sum_{i=1}^s f_i = 1$).

For two strata, with observed values for V_i, f_i , and δ_i the formula reduces to the following:

$$\hat{w}_1 = \frac{\hat{V}_2 + \hat{f}_1(\hat{\delta}_1 - \hat{\delta}_2)^2}{\hat{V}_1 + \hat{V}_2 + (\hat{\delta}_1 - \hat{\delta}_2)^2}, \quad \hat{w}_2 = 1 - \hat{w}_1.$$

The overall non-inferiority of this objective will be demonstrated if all 4 individual null hypotheses are rejected.

5.1.1.2.2 Statistical Method for Co-primary Objective 2

Each of the serogroups A, C, Y, and W will be tested separately. If the lower limit of the 2-sided 95% CI of the difference between the 2 percentages is $> -10\%$, the inferiority assumption will be rejected.

For the 4 non-inferiority hypotheses using the response rates (percentages of subjects who achieve an hSBA titer $\geq 1:8$), the CI of the difference in proportions will be computed using the Wilson Score method without continuity correction (3).

Let $\hat{\theta} = p_1 - p_2$, then $L = \hat{\theta} - \delta$ and $U = \hat{\theta} + \varepsilon$ are respectively the lower and the upper limits of the CI, where:

$$\delta = Z_{0.025} \sqrt{\left\{ \frac{l_1(1-l_1)}{n_1} + \frac{u_2(1-u_2)}{n_2} \right\}}$$

$$\varepsilon = Z_{0.025} \sqrt{\left\{ \frac{l_2(1-l_2)}{n_2} + \frac{u_1(1-u_1)}{n_1} \right\}}$$

l_1 and u_1 are calculated from the CI of the single proportion in Group 1 given by:

$$\frac{(2n_1p_1 + Z_{0.025}^2 \pm Z_{0.025} \sqrt{(Z_{0.025}^2 + 4n_1p_1(1-p_1))})}{2(n_1 + Z_{0.025}^2)}$$

l_2 and u_2 are calculated from the CI of the single proportion in Group 2 given by:

$$\frac{(2n_2p_2 + Z_{0.025}^2 \pm Z_{0.025} \sqrt{(Z_{0.025}^2 + 4n_2p_2(1-p_2))})}{2(n_2 + Z_{0.025}^2)}$$

where $Z_{0.025}$ is the upper 97.5th percentile of the standard normal distribution.

The overall non-inferiority of this objective will be demonstrated if all 4 individual null hypotheses are rejected.

To conclude, non-inferiority in toddlers who either are meningococcal vaccine-naïve or have received monovalent MenC vaccination during infancy and non-inferiority in meningococcal vaccine-naïve subjects have to be demonstrated.

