## 12.1.1 Hypotheses and Statistical Methods for Primary Objectives

Two co-primary objectives will be evaluated.

### 12.1.1.1 Primary Objective 1

***Non-inferiority testing after 1 dose of MenACYW conjugate vaccine or Nimenrix® in toddlers who either are meningococcal vaccine naïve or have received monovalent MenC vaccination during infancy***

The percentages of subjects who achieve an hSBA titer  $\geq 1:8$  for meningococcal serogroups A, C, Y, and W in toddlers who received MenACYW conjugate vaccine (Group 1 and Group 3) are non-inferior to the corresponding percentages in toddlers who received Nimenrix® (Group 2 and Group 4) 30 days post administration.

Null hypothesis ( $H_0$ ):  $p_{(\text{Men})} - p_{(\text{Nim})} \leq -10\%$

Alternative hypothesis ( $H_1$ ):  $p_{(\text{Men})} - p_{(\text{Nim})} > -10\%$

where  $p_{(\text{Men})}$  and  $p_{(\text{Nim})}$  are the percentages of subjects who achieve an hSBA titer  $\geq 1:8$  in the MenACYW vaccine group and the Nimenrix® group, respectively. Each of the serogroups A, C, Y, and W will be tested separately. If the lower limit of the 2-sided 95% confidence interval (CI) of the difference between the 2 percentages is  $> -10\%$ , the inferiority assumption will be rejected.

For the 4 non-inferiority hypotheses using the response rates (percentages of subjects who achieve an hSBA titer  $\geq 1:8$ ), the 95% CI will be stratified on the priming status (meningococcal vaccine naïve or primed monovalent MenC vaccination during infancy) and calculated using the Wald method (normal approximation). Weighted average of the difference over strata will be calculated using the Minimal Risk weights with the null variance method (43).

The overall non-inferiority of this objective will be demonstrated if all 4 individual null hypotheses are rejected.

### 12.1.1.2 Primary Objective 2

***Non-inferiority testing after 1 dose of MenACYW conjugate vaccine or Nimenrix® in meningococcal vaccine naïve toddlers***

Thirty days after the administration of MenACYW conjugate vaccine or Nimenrix®, the percentages of subjects who achieve an hSBA titer  $\geq 1:8$  for meningococcal serogroups A, C, Y, and W in Group 1 are non-inferior to the corresponding percentages in Group 2.

Null hypothesis ( $H_0$ ):  $p_{(G1)} - p_{(G2)} \leq -10\%$

Alternative hypothesis ( $H_1$ ):  $p_{(G1)} - p_{(G2)} > -10\%$

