3.1 Trial Design

This was a Phase III, modified double-blind, randomized, parallel-group, active-controlled, multi-center trial to compare the immunogenicity and describe the safety of a single dose of MenACYW conjugate vaccine to a single dose of a licensed quadrivalent meningococcal polysaccharide groups A, C, W-135, and Y conjugate vaccine, Nimenrix[®], in toddlers (12 to 23 months of age) in the EU who are either meningococcal vaccine naïve or received monovalent MenC vaccination during infancy.

Approximately 918 healthy toddlers aged 12 to 23 months were to be enrolled and randomized as follows depending on the meningococcal background:

Meningococcal Vaccine-Naïve Subjects: 612 subjects were to be randomized in a 1:1 ratio to the following 2 groups:

- Group 1: MenACYW conjugate vaccine (n=306)
- Group 2: Nimenrix[®] (n=306)

MenC-Primed Subjects: 306 subjects were to be randomized in a 2:1 ratio to the following 2 groups:

- Group 3: MenACYW conjugate vaccine (n=204)
- Group 4: Nimenrix[®] (n=102)

Enrollment of MenC-primed subjects was stratified by the type of primed vaccine, MenC-TT (NeisVac-C[®]) or MenC-CRM (Menjugate[®], Meningitec[®]), considering that at least 25% and a maximum of 50% of subjects had been primed with MenC-CRM as described in Table 3.1 below:

Table 3.1: MenC priming strategy

Priming	Group 3 MenACYW conjugate vaccine	Group 4 Nimenrix [®]
MenC-TT	102 - 152*	51 - 76*
MenC-CRM	52* - 102	26* - 51

Total	204	102
--------------	-----	-----

*Sample size corresponding to 25% of subjects primed with MenC-CRM

All subjects were to provide blood samples for immunogenicity assessment at baseline (pre-vaccination) and at 30 to 44 days post-vaccination.

Solicited adverse event (AE) information were to be collected for 7 days after vaccination, unsolicited AE information were to be collected from Visit (V) 01 (Day [D] 0) to V02 (D30 [+14 days]), and serious adverse event (SAE) information, [REDACTED] were to be collected throughout the trial.

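### The 95% CI for co-primary objective 1 takes its variance from the null, so at high response rates it covers more than 95%. The excess depends on rates the documents do not show, and the non-inferiority decision is unaffected.

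*SAP*

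**What the plan says.** SAP 5.1.1.1.1 sets the null for co-primary objective 1 as a difference, MenACYW minus Nimenrix, of −10 points or less. SAP 5.1.1.2.1 decides each serogroup by one interval: "If the lower limit of the 2-sided 95% confidence interval (CI) of the difference between the 2 percentages is" above −10%, inferiority is rejected. On stratification it says "the 95% CI will be stratified on the priming status (meningococcal vaccine naïve or primed monovalent MenC vaccination during infancy"), and the interval has Wald form.

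The formula is introduced by "two-sided CIs for the difference in proportions between two groups using the Minimum Risk Weights with the null variance are calculated as follows". It is the weighted difference plus or minus z times the root of the sum, over strata, of squared weight times null variance. The rates entering that variance "are the constrained maximum likelihood estimates (MLEs) of response rates" for the two vaccines in each stratum. The section does not print the value of the constraint.

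Protocol 12.1.1.1 names the same approach: "Weighted average of the difference over strata will be calculated using the Minimal Risk weights with the null variance method". Neither document reserves this interval for testing, and neither plans another confidence interval for the overall difference. The sample size sections (Protocol 12.5, SAP 5.5) are redacted, so the assumed response rates and attrition are not visible.

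**The concern.** A variance evaluated at a difference of −10 points is the right yardstick for asking whether the data are compatible with −10. It is not the right yardstick for limits that lie near zero. When both vaccines give high response, forcing the fitted rates 10 points apart pulls the MenACYW rate down to where binomial variance is much larger. The same enlarged standard error is then used for both limits.

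The result would be labelled a 95% interval and reported as the main estimate of precision for each serogroup. A reader would take the trial to be less precise than it is. It would also sit next to the Wilson score intervals of co-primary objective 2 (SAP 5.1.1.2.2) on a different footing, so the two sets could not be compared directly.

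**Working it through.** **Inputs**
- Null difference −10 points (SAP 5.1.1.1.1). I take it as the constraint, because that is the stated null.
- Planned sizes 306/306 naïve and 204/102 primed (SAP 3.1).
- 10% loss is my assumption: 0.9 × 306 = 275, 0.9 × 204 = 184, 0.9 × 102 = 92.
- Response rates are assumptions, taken as equal in both strata. MET54 (Protocol 1.2.2.2; naïve toddlers, same comparator and assay) gave 97.8 to 98.9% for MenACYW and 91.9 to 100.0% for Nimenrix on A, Y and W. For C it gave 100.0% and 89.5%. MET39 (Protocol 1.2.2.1; one dose at 12 months) gave 75%, 90%, 48% and 54% for A, C, Y and W.
- The difference is taken as MenACYW minus Nimenrix, as in the hypothesis. The SAP formula prints the reverse order, which is a separate point.

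**What can be reproduced.** The only visible figure is the nominal 95%. It is reproduced at the margin: with true rates of 88% and 98%, simulated coverage is 94.9% and one-sided error 2.4 to 2.5%.

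**Worked case, 98% in every arm**
1. Observed variances: naïve 0.98 × 0.02 × (2/275) = 0.0001425; primed 0.98 × 0.02 × (1/184 + 1/92) = 0.0003196.
2. Minimum-risk weight. With equal stratum differences the two-stratum formula reduces to w₁ = V₂/(V₁ + V₂) = 0.3196/0.4621 = 0.692, so w₂ = 0.308.
3. Rates constrained to −10 points: naïve 88.95% and 98.95%; primed 89.29% and 99.29%.
4. Null variances, p(1−p)/n summed over arms: naïve 0.000395, primed 0.000597.
5. SAP standard error: √(0.692² × 0.000395 + 0.308² × 0.000597) = 0.01568. Half-width 1.96 × 1.568 = 3.07 points.
6. Observed-variance standard error: √(0.692² × 0.0001425 + 0.308² × 0.0003196) = 0.00993. Half-width 1.95 points.
7. Coverage ≈ 2Φ(1.96 × 1.568/0.993) − 1 = 2Φ(3.09) − 1 = 99.8%. Simulation of the SAP formula also gives 99.8%.

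**Other rates, by simulation at 275/275/184/92** (half-widths in points)

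| MenACYW / Nimenrix | SAP half-width | Observed-variance half-width | SAP coverage |
|---|---|---|---|
| 98 / 98 | 3.1 | about 1.9 | 99.8% |
| 95 / 95 | 3.5 | 3.0 | about 97.7% |
| 90 / 90 | 4.3 | 4.1 | 95.4% |
| 98.0 / 91.9 | 3.8 | 3.1 | about 98% |
| 99.5 / 89.5 (C in MET54, 100% taken as 99.5%) | 3.9 | 3.2 | about 98% |
| 48 to 75, equal (MET39) | no material difference | no material difference | about 95% |

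**If the constraint were 0.** Coverage at 98% would be about 95%.

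**Score interval by inversion, same weights, at the expected counts.** It is −2.05 to +2.24 points at 98% and −3.05 to +3.23 at 95%. Its coverage is about 95%.

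**Set beside co-primary objective 2.** At the planned sizes with 98% everywhere, the objective 1 interval from 918 subjects is ±2.91 points. The objective 2 Wilson interval from 612 subjects is ±2.51. The larger sample gives the wider interval.

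**The case against.** The strongest reply is that the interval exists to be compared with −10, and there it works. One-sided error at 88% against 98% is 2.4 to 2.5%, while the observed variance gives 3.0 to 3.1%. Power at 98% is about 100%. The method is the same in protocol and SAP, and where it errs at high response it errs on the wide side. All of this stands. A reader might infer that the non-inferiority conclusion is unsafe; the documents and the figures do not support that.

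A reader might also infer that all four intervals cover 99.8%. That is not supported either. Equal rates near 98% are an assumption. In MET54, Nimenrix was lower for C and for at least one of A, Y and W, and there the excess is about 0.7 to 0.8 points of half-width. MET54 enrolled naïve toddlers only, so no rate for the primed stratum is visible. At MET39 rates of 48 to 75% there is no excess.

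The constraint value is indeed not printed, and a value of 0 would remove the problem. But 0 is not the stated null, so if it was meant, the SAP still has to say so.

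Finally, neither document plans a tighter margin or pooling, and group percentages with exact intervals will let others compute their own interval. That limits the harm. It does not make a 95% label right on the only planned interval for this difference.

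**Conclusion.** The point holds in conditional form. If the constraint is the stated −10 points, the interval reported for co-primary objective 1 is a valid test device, but its coverage exceeds 95% when response is high and the true difference is away from −10. The range runs from about 95% coverage (rates of 90% or lower) through about 98% (MET54-like unequal rates) to 99.8% (98% in all arms, half-width 3.1 against about 1.9 points). These figures rest on 10% loss, the same rates in both strata, and response rates borrowed from earlier studies because the planning rates are redacted. The fault lies in the reported precision only; no non-inferiority decision changes.

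**What to change.** In SAP 5.1.1.2.1:
- State that the constrained estimates are computed at a difference of −10 points, and keep that null variance for the test.
- Report as the 95% CI the set of values d for which |estimate − d| / √(Σ w² V₀(d)) ≤ 1.96. Recompute the constrained estimates at each d and use the same minimum-risk weights.
- Have the routine confirm that this set is a single interval. It was in the cases checked. Given that, the lower limit exceeds −10 exactly when the test rejects, so the decision is preserved.

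A plain Wald interval with the observed variance is not a good substitute. At the planned sizes it covers 94.0 to 94.6% at 98% response, and its one-sided error at 88% against 98% is 3.0 to 3.1%.

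The cost is SAP wording and a short iterative routine, with no new data.
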